CRA	Clinical Research Associate
CRF	Case Report Form
CYP2B6 gene	CYP2B6 gene encodes the Cytochrome P450 class of metabolic enzymes found mainly in the human liver. It metabolizes ketamine, controlling how fast ketamine is eliminated from the body.
DISC1 gene	Disrupted in Schizophrenia 1 genotype. Well established as a genetic risk factor across a spectrum of psychiatric disorders. DISC1 is highly expressed during critical brain development periods.
DSM-V	Diagnostic and Statistical Manual of Mental Disorders, 5 th Edition
EEG	Electroencephalogram
Electrode	Conductor through which electricity enters or leaves
Endophenotype	A quantitative biological trait that is reliable in reflecting the function of a discrete biological system and it is reasonably heritable. It is also known as an intermediate phenotype. It is more closely related to the root cause of a disease than a broad, clinical phenotype.

GCP	Good Clinical Practice. This is a standard for the design, conduct, performance, monitoring, auditing, recording, analyses, and reporting of clinical trials that provides assurance that the data and reported results are credible and accurate, and that the rights, integrity and confidentiality of trials participants are protected.
HAM-D	Hamilton Depression Rating Scale. Widely used clinician-administered depression assessment scale.
HIPAA	Health Insurance Portability and Accountability Act
HPA Axis	Hypothalamic-Pituitary-Adrenal axis – central stress response system
HTR2A gene	HTR2A serotonin gene influences the serotonin 5-HT2A receptor pathway
ICH	International Council for Harmonisation of Technical Requirements for Pharmaceuticals for Human Use. This is an international body that sets guidelines for clinical research.
ICMJE	International Committee of Medical Journal Editors. A group of general medical journal editors and representatives of selected related organizations working together to improve the quality of medical science and its reporting.
IRB	Institutional Review Board. This is an independent body constituted of medical, scientific, and non-scientific member whose responsibility is to ensure the protection of the rights, safety and well-being of human participants involved in a clinical trial. Also known as the ethics committee.
Ketamine	Belongs to a class of drugs known as dissociative anesthetics. It is a noncompetitive NMDAR antagonist.
MDD	Major Depressive Disorder
Met/Met COMT gene	Slow variation of the COMT gene associated with greater levels of cortisol and HPA axis dysfunction
NMDA	N-Methyl-D-aspartate
NMDAR	N-Methyl-D-aspartate receptor. It is a glutamate-gated cation channel critical for development of Central Nervous System (CNS) and neuroplasticity.
NRG1 gene	Neuregulin 1 gene stimulates cell proliferation and differentiation, including neurite output and myelin production. Over expression results in disrupted excitatory-inhibitory connections, reduced synaptic plasticity and abnormal

	dendritic spine growth. Under expression is linked to various autoimmune disorders.
PMQ-SF	Psychedelic Music Questionnaire Short Form. The PMQ-SF assess the impact of music on patients receive Ketamine for treatment resistant depression. It looks at measures of mood, anxiety, suicidality and psychological/physical pain through the rating of 15 statements and then 2 free answer questions.
PTSD	Post-Traumatic Stress Disorder
QIDS-SR 16	The Quick Inventory of Depressive Symptomatology- Self Report. The QIDS-SR 16 is derived from the 30-item Inventory of Depressive Symptomatology (IDS). It has 16 items that assess nine DSM-IV diagnostic symptom domains: sad mood, poor concentration, self-criticism, suicidal ideation, anhedonia, energy/fatigue, sleep disturbance, decrease/increase in appetite/weight, and psychomotor agitation/retardation
SAE	Serious Adverse Event defined as an adverse event that either: causes death; is life-threatening; causes hospitalization or prolongs existing hospitalization; results in persistent or significant disability/incapacity; is a congenital anomaly/birth defect
SOC	Standard of Care

1. Introduction

1.1 Rationale

This observational study will allow data to be collected to demonstrate changes in brain activity following administration of standard of care (SOC) Ketamine. By comparing genetic markers across participants, data on impact of genetic markers and response to Ketamine will also be analysed. This data will contribute to the design of future studies utilizing Ketamine for various psychiatric disorders. This study will focus on treatment-resistant Major Depressive Disorder (MDD).

1.2 Background

Ketamine traditionally has been used as an anesthetic. It is a NMDA receptor antagonist which has rapid and potent antidepressant effects in treatment-resistant Major Depressive Disorder and Bipolar Depression. Ketamine treatment is used for hard-to-treat depression, post-traumatic stress disorder (PTSD) and other psychiatric disorders. These disorders are accompanied by abnormal brain activity with emotional alteration. Ketamine has widespread effects on brain activity of individuals who are resistant to other treatments for psychiatric disorders such as anxiety, PTSD and depression (Blanke, 2009; Iadarola, 2016).

Electroencephalogram (EEG) is a test used to record electrical activity in the brain. Brain cells communicate utilizing electrical impulses. The EEG uses electrodes on the scalp to measure the brain wave patterns and records them. The EEG is a safe procedure having been used for many years, causing no discomfort to the participant. The electrodes record brain activity but do not produce any sensation and there is minimal risk of getting an electric shock as there is no current being directly delivered to the participant. EEG has high temporal specificity with an ability to pinpoint the exact source, making it an excellent tool for this clinical study (Hubbard, 2019).

Conventionally, a wet electrode EEG system is utilized. Wet electrodes rely on conductive gel to record the brain waves. They are messier to use and require a trained EEG technician for application. Dry electrode EEG systems have up to 20 conductive pins per electrode and the pins are coated with either silver, gold or nickel. The dry electrodes do not need any gel application which makes it easier to apply and do not require as much training. This study proposes to utilize Zeto EEG system, a dry, wireless system.

Previous research has linked prefrontal EEG patterns to Ketamine effects in patients with diagnosed treatment-resistant depression (Cao, 2019). Genetic markers may play a role in the brain reactions to Ketamine. Several EEG parameters are potential endophenotypes when looking at different psychiatric disorders (Malone 2014). Researchers utilized cheek swabs to assess which markers contributed most to a decrease in absolute HAM-D scores and determined the 'Met/Met' variant of the COMT gene was the best genetic predictor of treatment outcome (Spronk 2010).

There are inter-individual genetic variations to psychedelic drug effects. Testing for specific genetic markers helps determine the effects expected. This study will look at the following five genetic markers:

- HTR2A
- CYP2B6 gene
- C4A and C4B genes
- NRG1 gene
- DISC1 gene

This observational study will observe genetic markers and EEG patterns from pre, during and post Ketamine administration.

2. Objectives and Purpose

The objective of this observational study is to determine the effects of routine, intramuscular, clinically administered Ketamine on the brain's electrical activity and biomarkers. The brain activity will be measured with an EEG electrode cap and the biomarkers will be collected via a cheek swab.

2.1 Primary Objective

The primary objective is to study what baseline EEG measures and genetic markers predict a Ketamine treatment response among participants with treatment-resistant Major Depressive Disorder.

2.2 Secondary Objectives

The secondary objectives are to:

- Evaluate neurological changes during Ketamine sessions via EEG
- Evaluate persistent neurological changes in a follow up session post-treatment
- Identify biomarkers based on neurological changes during Ketamine sessions via cheek swab

3. Study Description

This is an Open Label Observational Study with the primary objective to assess brain activity in patients prior to, during and after Ketamine treatment and to assess genetic markers prior to Ketamine treatment. This is a non-interventional study that will observe the EEG pattern of participants who, per standard of care, are treated with intramuscular Ketamine. The administration of the Ketamine during this study is not considered investigational. The experimental intervention, measurements via EEG, will be offered to patients of the study

site presenting for intramuscular (IM) ketamine treatment per the site's established and evidence-based protocol as part of their regular clinical care. Participants in this study have already been determined to have a medically appropriate indication for IM Ketamine treatment, independent of enrollment in this study. Given the requirement, per study protocol, to wear an EEG headset, permit a video recording of the session and complete study measures, participants will be compensated by having treatment costs paid by the study sponsor.

There will be 36 participants enrolled.

4. Scheduling of Visits

All visits will occur at the clinic of the principal site investigator. The study will enrol for approximately 3-4 months. All times should be recorded using the 24-hour clock.

4.1 Discontinuation or Participant Withdrawal

Participants may withdraw at any time from the study under the following circumstances:

- Withdrawal of informed consent
- Lost to follow-up
- Serious adverse event occurs
- In the opinion of the investigator, the participant should be withdrawn

5. Study Population

5.1 Inclusion Criteria

1. Primary DSM-V diagnosis of treatment-resistant Major Depressive Disorder (may have secondary diagnoses of general anxiety, substance disorder)
 - Non-responders to at least 2 previous anti-depressant medications prescribed by a physician in the past five years
 - Score of ≥ 20 on Montgomery-Asberg Depression Rating Scale (MADRS) (i.e., moderate to severe depression)
2. All genders aged 21 to 60 years of age
3. Prescribed Ketamine or currently being treated with Ketamine for treatment-resistant Major Depressive Disorder
4. Willing to wear an EEG headset and an eye mask
5. Willing to permit a digital video recording to be collected for safety monitoring
6. Willing to listen to ambient sound
7. Willing to have a genetic cheek swab

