5.2 Exclusion Criteria

1. Pregnancy
2. Traumatic Brain Injury within past 3 months
3. Body weight < 50 kg or > 120 kg
4. Coronary heart disease
5. Uncontrolled hypertension as defined in the ACC/AHA Hypertension Guidelines
6. Previous contact with Ketamine (therapeutically or recreationally) outside of treatment at the study site
7. Primary psychotic disorder (e.g., schizophrenia, schizoaffective disorder)
8. Bipolar disorder with current manic, hypomanic or mixed state
9. Post-traumatic stress disorder
10. Obsessive-compulsive disorder
11. Primary substance-use disorder
12. Alcohol consumption 24 hours prior and 48 hours subsequent to treatment
13. Currently using any of the following medications:
 - Benzodiazepines for 6 hours prior to treatment and 2 hours after treatment
 - Lamotrigine for 6 hours prior to treatment
 - Amphetamine-based stimulants for 6 hours prior to treatment
 - MAO-Is may be taken but blood pressure must be monitored

6. Study Procedures

	Screen V1	V2	V3-V11	V12
	Day 0	Day 1 (±1 day) Session 1	Days 3, 5, 8, 11, 18, 25, 32, 46, 67 (±2 days) Sessions 2-10	Day 74 ± 2 days
Eligibility criteria	X			
Informed Consent	X			
Medical History and current medical conditions	X			
Urine HCG Pregnancy Test	X			
Demography	X			
Cheek Swab ¹		X		
Questionnaires ² (CADSS-6, QIDS-SR-16, PMQ-SF)		X	X ²	X
EEG applied ³		X	X	
EEG measured 5 ±2 min eyes closed/ 5 ±2 min eyes open prior to session		X	X	X
Wavepaths music track played		X	X	
EEG recording prior to injection and through to 15 minutes after end of session ³		X	X	
Ketamine Injection (SOC) ⁴		X	X	
Adverse Events		X	X	X
Concomitant Medications	X	X	X	X

¹ Cheek swab for testing of genetic markers and questionnaires are done directly prior to the first session beginning.

² Questionnaires to be administered at first and last sessions as well as at day 74 only for a total of 3 times each

³Sessions are approximately 60 minutes in duration, EEG is continuous for approximately 75 minutes. A digital video recording will be collected at each visit for safety monitoring.

⁴ There are a total of 10 sessions per participant over a span of 67 days

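### Patients already on Ketamine at the study site may enrol, so their Session 1 EEG and QIDS-SR-16 are not pre-Ketamine values, and the plan does not describe or separate them

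*Combined protocol and SAP*

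**What the plan says.** **Eligibility.** Section 5.1, item 3, admits patients who are "Prescribed Ketamine or currently being treated with Ketamine for treatment-resistant Major Depressive Disorder". Section 5.2, item 6, excludes "Previous contact with Ketamine (therapeutically or recreationally) outside of treatment at the study site". Section 5.1, item 1, also requires a MADRS score of at least 20. No section sets a washout, requires patients to be Ketamine-naive, or says how sessions received before enrolment are counted.

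**Schedule.** In the Section 6 table the first EEG is at Visit 2 (Session 1). Footnote 2 reads "Questionnaires to be administered at first and last sessions as well as at day 74 only for a total of 3 times each". Section 6.1 gives a different count of occasions, but it too puts the first one at Session 1. Medical history is taken at screening and "Concomitant Medications" has a row at every visit. Neither the number of earlier Ketamine sessions nor the date of the last one is a specified item.

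**Aims.** Section 2.1 asks "what baseline EEG measures and genetic markers predict a Ketamine treatment response". Section 3 sets out to "assess brain activity in patients prior to, during and after Ketamine treatment and to assess genetic markers prior to Ketamine treatment". Section 2.2 includes the aim "Evaluate persistent neurological changes in a follow up session post-treatment".

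**The word baseline.** Section 10.1 sets baseline brain activity apart from changes during sessions. Sections 6.2 and 7 apply the term to the recording made before the music and the injection at sessions generally.

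**Analysis.** Section 10.2 gives descriptive statistics. Section 10.3 makes inter- and intra-patient variability the primary outcome and lists correlations of neurological phenotypes with genotype and the questionnaires, without time points. Prior exposure appears in none of Sections 10.1 to 10.3.

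**The concern.** The predictor in the primary objective is baseline EEG. If some patients start Session 1 partway through a Ketamine course and others start untreated, that predictor mixes two states. Two consequences follow.

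- A difference in Session 1 EEG between the two kinds of patient widens between-patient variability, which is half of the primary outcome.
- If the two kinds of patient also differ in later QIDS change, an unadjusted correlation of Session 1 EEG with QIDS change is pushed up or down, depending on the signs of the two differences.

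The protocol lists persistent neurological change as something still to be evaluated, so it cannot take absence of carry-over for granted. Genotype is not altered by earlier treatment, but the EEG or response it is correlated with may be.

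**Working it through.** **Step 1: the text.** Item 3 of the inclusion criteria has two entry routes, newly prescribed or currently treated. Exclusion 6 closes the second route only for Ketamine received outside the site. A patient in mid-course at the site therefore passes both. The earliest EEG and QIDS-SR-16 are at Session 1, so nothing in the schedule precedes that patient's first Ketamine dose. The ten sessions over 67 days describe the study schedule; they are not an entry condition.

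**Step 2: inputs for a size.** The only figure in the documents is 36 participants. It comes with no alpha, power, effect size or SD, so it cannot be reproduced. The documents also give no pretreated share, EEG carry-over, QIDS difference or definition of response. Everything below is assumed: k pretreated of 36; an EEG shift s of 0.5 to 1 within-group SD; a difference d of 3 to 6 points in QIDS improvement; and a within-group SD of QIDS change of 5 points. Put p = k/36 and v = p(1 − p).

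**Step 3: between-patient SD of Session 1 EEG.** Inflation factor = √(1 + v·s²).

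- k = 4: v = 0.0988; factor √1.0247 = 1.012 (s = 0.5) to √1.0988 = 1.048 (s = 1).
- k = 18: v = 0.25; factor √1.0625 = 1.031 to √1.25 = 1.118.

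For scale, the relative standard error of an SD at n = 36 is 1/√(2 × 35) = 0.120.

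**Step 4: correlation of Session 1 EEG with QIDS change.** The plan does not state this analysis; it is one reading of Section 2.1. With within-group correlation ρ:

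r = (5ρ + v·s·d) / √[(1 + v·s²)(25 + v·d²)]

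With ρ = 0:

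| k | s = 0.5, d = 3 | s = 1, d = 6 |
|---|---|---|
| 1 | 0.008 | 0.031 |
| 2 | 0.015 | 0.059 |
| 4 | 0.029 | 0.106 |
| 9 | 0.053 | 0.183 |
| 18 | 0.070 | 0.230 |

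All of these lie inside the 95% interval around zero at n = 36, which is ± tanh(1.96/√33) = ± 0.33.

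With ρ = 0.40, the first figure is for shifts in the same direction and the second for opposing shifts (v·s·d negative):

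- k = 4, low inputs: 2.148/5.151 = 0.42, or 1.852/5.151 = 0.36.
- k = 4, high inputs: 2.593/5.601 = 0.46, or 1.407/5.601 = 0.25.
- k = 18, low inputs: 2.375/5.381 = 0.44, or 1.625/5.381 = 0.30.

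**Step 5: does adjustment help?** In a simulation with n = 36, 40,000 runs, s = 1 and |d| = 6, the correlation adjusted for prior exposure averages 0.39 to 0.40 when the within-group correlation is 0.40 in both groups. If it is 0.40 in naive and 0 in pretreated patients, the adjusted value averages 0.36, 0.30 or 0.20 with 4, 9 or 18 pretreated. Adjustment therefore relies on similar within-group correlations.

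**The case against.** The strongest reply has four parts.

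- **The correlation is not a planned analysis.** Section 10.2 is descriptive, Section 10.1 speaks of feasibility, and Section 10.3 gives no time points. This stands: the correlation figures are conditional on someone relating baseline EEG to QIDS change.
- **The MADRS floor limits the problem.** A score of at least 20 at entry keeps out patients who are currently well on Ketamine, and this probably lowers the number of pretreated entrants. It does not make the remainder naive, and it may favour those who have responded poorly so far.
- **Every session has its own pre-injection EEG.** This is a usable reference for acute within-session change, and it matches how Sections 6.2 and 7 use baseline. It does not supply a pre-treatment value for predicting response.
- **Mixed enrolment is daily practice.** Section 10 defends the design on that ground. This stands too, and it is why eligibility is left alone here.

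A reader might go further and infer that a real association between EEG and response could be nearly hidden. That needs half the sample pretreated, a full 1 SD EEG shift, a 6-point QIDS difference and opposing signs all at once; the documents support none of these inputs. Nor do they show that carry-over distorts within-session change or intra-patient variability. They only leave it open.

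**Conclusion.** The point holds as a gap between eligibility and aims. As written, the plan cannot give a pre-Ketamine EEG or QIDS-SR-16 for patients already treated at the site, and it neither specifies their exposure as data items nor separates them in the analysis. That the analysis would pool all 36 is inferred from the absence of any split; the plan does not say so.

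The size is unknown because the number of such patients is unknown. With 1 or 2 the effect is negligible. With 4 to 18, under the assumed shifts, the between-patient EEG SD is inflated by about 1 to 12%, and the top of that range is about one standard error of an SD at this sample size. The documents do not support a claim that the primary outcome is seriously biased, or that pretreated patients must be kept out. The matter should be settled because it is cheap to record now and harder to reconstruct later from general history entries.

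**What to change.** 1. At Visit 1, record from site records the number of earlier Ketamine sessions and the date of the last one, and tabulate both.
2. Report Session 1 EEG and its between-patient variability by prior exposure (naive yes or no), labelled descriptive.
3. If baseline EEG is related to QIDS change, adjust for prior exposure, state the assumption of equal within-group correlations, and show the Ketamine-naive subset as a sensitivity analysis.
4. Reconcile Sections 2.1, 3, 5.1, 5.2, 6.2, 7 and 10.1 on what baseline means. No change to eligibility is needed.

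**Cost.** Two CRF fields and one degree of freedom. The plan sets no test, so take 80% power and two-sided 5% as an assumed reference. The detectable correlation at n = 36 moves from tanh(2.80/√33) = 0.45 to tanh(2.80/√32) = 0.46. Subgroup estimates will be imprecise: in a naive subset the detectable correlation is tanh(2.80/√24) = 0.52 at n = 27 and tanh(2.80/√15) = 0.62 at n = 18, so that subset can serve only as a sensitivity analysis. If no pretreated patient enrols, the two fields show it and the matter is closed.

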5.2 Exclusion Criteria

1. Pregnancy
2. Traumatic Brain Injury within past 3 months
3. Body weight < 50 kg or > 120 kg
4. Coronary heart disease
5. Uncontrolled hypertension as defined in the ACC/AHA Hypertension Guidelines
6. Previous contact with Ketamine (therapeutically or recreationally) outside of treatment at the study site
7. Primary psychotic disorder (e.g., schizophrenia, schizoaffective disorder)
8. Bipolar disorder with current manic, hypomanic or mixed state
9. Post-traumatic stress disorder
10. Obsessive-compulsive disorder
11. Primary substance-use disorder
12. Alcohol consumption 24 hours prior and 48 hours subsequent to treatment
13. Currently using any of the following medications:
 - Benzodiazepines for 6 hours prior to treatment and 2 hours after treatment
 - Lamotrigine for 6 hours prior to treatment
 - Amphetamine-based stimulants for 6 hours prior to treatment
 - MAO-Is may be taken but blood pressure must be monitored

6. Study Procedures

	Screen V1	V2	V3-V11	V12
	Day 0	Day 1 (±1 day) Session 1	Days 3, 5, 8, 11, 18, 25, 32, 46, 67 (±2 days) Sessions 2-10	Day 74 ± 2 days
Eligibility criteria	X			
Informed Consent	X			
Medical History and current medical conditions	X			
Urine HCG Pregnancy Test	X			
Demography	X			
Cheek Swab ¹		X		
Questionnaires ² (CADSS-6, QIDS-SR-16, PMQ-SF)		X	X ²	X
EEG applied ³		X	X	
EEG measured 5 ±2 min eyes closed/ 5 ±2 min eyes open prior to session		X	X	X
Wavepaths music track played		X	X	
EEG recording prior to injection and through to 15 minutes after end of session ³		X	X	
Ketamine Injection (SOC) ⁴		X	X	
Adverse Events		X	X	X
Concomitant Medications	X	X	X	X

¹ Cheek swab for testing of genetic markers and questionnaires are done directly prior to the first session beginning.

² Questionnaires to be administered at first and last sessions as well as at day 74 only for a total of 3 times each

³Sessions are approximately 60 minutes in duration, EEG is continuous for approximately 75 minutes. A digital video recording will be collected at each visit for safety monitoring.

⁴ There are a total of 10 sessions per participant over a span of 67 days

6.1 Questionnaires

Several trait- and state-related questionnaires will be administered at the beginning of the first and last session. Each questionnaire will be given on 2 occasions:

